Clinical Trial PRS Application

Research Title:

The effectiveness of **enhancing self-care abilities** for agriculture and aquaculture workers diagnosed with **cardiometabolic diseases**

IRB No.: **202301844B0**

English Synopsis: 2023/12/01

English Abstract

Background: Community care emphasizes the three-tier, five-level preventive strategy and is also expected to demonstrate innovative capabilities and advocacy in promoting health equity within sustainable development and adapting to climate change. Agriculture and aquaculture form the cornerstone of a nation's important development, the livelihood of its people, and the conservation of its ecology. The southwest coastal regions of our country serve as a crucial hub for providing high-quality agricultural and fishery products to the nation, encompassing over one-third of the households and population engaged in agriculture and aquaculture nationwide. However, due to international economic and trade pressures and climate change, the number of agricultural and fishery workers (farmers and fishermen) has been gradually declining as they face reduced production capacity and income challenges. Based on our team's preliminary research findings, the prevalence and mortality rates of cardiovascular and metabolic diseases among agricultural and fishery workers in the southwest coastal regions are higher compared to the national average and advanced countries in Europe and America. Additionally, there is a higher incidence of chronic dehydration. Moreover, the overall educational level among these workers tends to be lower, the population is aging, and there is relatively inadequate access to medical resources. The literature indicates that individuals with cardiovascular and metabolic diseases can prevent health deterioration, such as myocardial infarction and stroke, by enhancing their self-care capabilities. From the perspective of aiding the sustainable development of agriculture and fisheries, how to overcome the health inequality resulting from societal determinants of health? The focus of this project is to enhance self-care capabilities effectively and address chronic dehydration by providing innovative strategies that align with their socioeconomic background. Our team's efforts in identifying, referring, and treating the high prevalence of hepatitis C virus in this region have gradually decreased the occurrence of liver cancer and other related cancers. Additionally, we have provided the Ministry of Agriculture with health needs and policy advocacy for farmers and fishermen, earning significant trust and attention from relevant authorities. This will aid us in continuing to promote interdisciplinary collaboration effectively. To date, there is a significant lack of domestic and international literature discussing and improving the health issues of farmers and fishermen. Research on community care aimed at preventing and alleviating the exacerbation of cardiovascular and metabolic diseases among this population is particularly scarce. **Research Purposes:** Therefore, based on the preliminary research

findings, this project will focus on the following investigations: (1) the self-care capabilities of farmers and fishermen with cardiovascular and metabolic diseases; (2) designing educational materials and tools tailored to the socioeconomic background of farmers and fishermen to enhance their self-care abilities; (3) validating the effectiveness of these educational materials and tools. These validations will serve as a basis for collaboration with local governments and private enterprises in academia-industry partnerships, aiming to expand the impact and diffusion of benefits. **Research Method and Objects:** This project will be based on nursing scholar Dorothea Orem's self-care theory, integrating the concept of the [life essential 8, LE8] proposed by the American Heart Association, as well as our team's recent research findings. We aim to develop educational materials and tools tailored for this group, termed [Self-Care Eight Essentials] aligning with these theories and previous research outcomes. This project is expected to be completed within three years. The first year will involve a cross-sectional descriptive study targeting farmers and fishermen in the southwest coastal regions. Collaborating with the local health bureau and regional hospitals, the study aims to identify farmers and fishermen already affected by cardiovascular and metabolic diseases. It will investigate their self-care abilities, chronic dehydration, and associated influencing factors. The estimated sample size is approximately 338 individuals. The research methods for the second and third years involve: (1) Developing a tabletop game educational tool tailored to the socioeconomic and cultural needs of farmers and fishermen, and training designated educators; (2) Employing a community-based quasi-experimental research design. Eligible participants will be cluster-randomized into intervention and control groups. Both groups will receive educational materials from the [Self-Care Eight Essentials (SC-8)]. The intervention group will additionally engage with the [SC-8 Monopoly-style board game] intervention, while the control group will follow the regular community care model. The study will assess the differences in self-care abilities, cardiovascular and metabolic markers, and inflammation indicators between the two groups. This phase anticipates an estimated sample size of around 205 individuals for each group.

Analysis: The study will employ both descriptive and inferential statistical analyses, such as chi-square and analysis of variance (ANOVA), multivariate linear regression, logistic regression, and generalized estimating equations (GEE) to handle repeated measures data and adjust for the effects of influencing factors. **Expected Outcomes:** This study aims to present an overview of self-care abilities among farmers and fishermen with cardiovascular and metabolic diseases, identifying the distance from the ideal level and related influencing factors. It intends to establish self-care educational materials and tools tailored to the socioeconomic background of this specific population. Additionally, the study aims to transform these materials into tabletop game educational tools that possess credibility, effectiveness, and an element of entertainment. Through patents and

technology transfer, these tools are expected to serve as convenient and effective guidance instruments for health bureaus and primary healthcare units.

Keywords: cardiometabolic diseases、agriculture、aquaculture、self-care、dehydration status、inflammatory biomarkers、board game、sustainable development goals、climate change、reduced inequalities。

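### The trial allocates by cluster, but the Analysis text gives no method the task of handling correlation within clusters

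*Protocol*

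**What the plan says.** The Research Method and Objects text of the English Abstract describes the second- and third-year trial: "Eligible participants will be cluster-randomized into intervention and control groups". The comparison follows: "The study will assess the differences in self-care abilities, cardiovascular and metabolic markers, and inflammation indicators between the two groups". The size is counted in people: "This phase anticipates an estimated sample size of around 205 individuals for each group". No number of clusters, cluster size or ICC is given.

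The Analysis text lists chi-square, ANOVA, multivariate linear regression, logistic regression and "generalized estimating equations (GEE) to handle repeated measures data and adjust for the effects of influencing factors". The methods are introduced as examples, so the list is not closed, and it serves both the first-year survey and the trial. Nowhere does the document mention a design effect, a cluster random effect, cluster-robust errors, a cluster-level analysis or the unit of analysis.

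**The concern.** Allocating whole clusters makes the outcomes of people in one cluster part of the same random draw. If those people resemble each other, 205 people carry less information about the group difference than 205 independent people would. A person-level analysis ignores this, and its standard errors come out too small.

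The Analysis text states what its methods are for, and the only dependence it names is repeated measurement. That points naturally to GEE grouped by person, which leaves correlation between people in the same cluster untouched.

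A board game with no effect could then be declared effective more often than the nominal rate. The protocol intends the validation to support collaboration with local governments and private enterprises, and expects the tools to reach health bureaus and primary care units. A false positive would therefore be acted on.

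**Working it through.** **1. Do the stated purposes cover the cluster?** There are two: repeated measures and adjustment for influencing factors.

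- *Repeated measures* is correlation within a person. It must refer to the trial, because the survey has none: "The first year will involve a cross-sectional descriptive study targeting farmers and fishermen in the southwest coastal regions".
- *Influencing factors* appears in the survey description: "It will investigate their self-care abilities, chronic dehydration, and associated influencing factors". There it means what is associated with self-care and dehydration, not the unit of allocation.

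Whether the purposes attach to GEE alone or to the whole list, correlation within clusters is not among them.

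**2. The plan's own figure.** The 205 per group cannot be reproduced: no significance level, power, effect size, standard deviation, dropout rate, cluster number or ICC is given. It is used below only as the number of people per group.

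**3. Assumptions.** Two-sided 5%; k = 5, 10 or 20 equal clusters per group, so m = 205/k = 41, 20.5 or 10.25; ICC 0.01 to 0.05; within-person correlation 0.5. None of these is in the protocol.

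**4. Person-level comparison at one time point.** DEFF = 1 + (m − 1) × ICC, and actual error = 2 × [1 − Φ(1.96/√DEFF)].

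For k = 5 and ICC 0.05: DEFF = 1 + 40 × 0.05 = 3.00; 1.96/√3.00 = 1.13; error 25.8%.

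| Clusters per group | ICC 0 | ICC 0.01 | ICC 0.05 |
|---|---|---|---|
| 5 | 5.0% | 9.8% | 25.8% |
| 10 | 5.0% | 7.3% | 16.3% |
| 20 | 5.0% | 6.1% | 10.5% |
| 41 (of 5 people) | 5.0% | 5.5% | 7.4% |

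Simulated person-level t-tests (20,000 trials per setting) agree: 9.6% and 25.8% for 5 clusters at ICC 0.01 and 0.05.

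**5. Person-level change from baseline.** Stable cluster effects cancel. With cluster autocorrelation c (the correlation of a cluster's effect between the two times),

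ICC of change = 2·ICC·(1 − c) / [2·ICC·(1 − c) + 2·(1 − ICC)·(1 − 0.5)].

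For k = 5, ICC 0.05, c = 0.8: 0.02/(0.02 + 0.95) = 0.0206; DEFF = 1 + 40 × 0.0206 = 1.825; error 14.7%.

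| c | Error, k = 5, ICC 0.05 | Range over k = 5–20, ICC 0.01–0.05 |
|---|---|---|
| 1.0 | 5.0% | 5.0% |
| 0.95 | 7.5% | 5.1–7.5% |
| 0.8 | 14.7% | 5.4–14.7% |
| 0.5 | 25.8% | 6.1–25.8% |

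**6. Do the remedies hold their level?** Simulated type I error at one time point (k 5–20, ICC 0–0.05, 20,000 runs per cell), with a t reference on 2k − 2 degrees of freedom:

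| Method | Near-equal cluster sizes | Size CV 0.4 |
|---|---|---|
| GEE by cluster, Mancl-DeRouen variance | 3.3–4.5% | 3.3–4.6% |
| GEE by cluster, Kauermann-Carroll variance | 4.8–5.2% | 5.1–6.0% |
| Mixed model (REML) | 1.6–4.8% | 1.4–5.1% |
| t-test on cluster means | 4.8–5.2% | 4.6–5.2% |

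Without the small-sample step (near-equal sizes), GEE by cluster gives 11.6–11.8% with 5 clusters per group, 7.9–8.3% with 10 and 6.3–6.5% with 20. The mixed model with a normal reference reaches 8.2%, 6.3% and 5.5%.

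Simulated change between two time points, k = 5, ICC 0.05, c = 0.8: GEE by person 15.0%; mixed model with cluster and person effects but no cluster-by-time effect 14.9%; with cluster-by-time and t 3.9%; t-test on cluster-mean change 5.0%. Over two time points, cluster-grouped GEE with t gave about 3–5% with Mancl-DeRouen and about 5% with Kauermann-Carroll.

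**The case against.** The strongest objection is scope. The document is a synopsis whose analysis text is one sentence, and the statistical analysis plan is not shown. How GEE is grouped, the unit of analysis and small-sample corrections are commonly settled there. The method list is open, GEE grouped by cluster would handle both correlations, and the person-level tests have a proper place in the survey. On this view the text is incomplete, not wrong.

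Much of that stands: the text does not show that clustering will be ignored. But the protocol is not silent on analysis. It names methods and states their purposes, and those purposes leave out the one dependence that its own allocation creates. That is a mismatch between design and analysis, not just an unwritten detail.

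It is also fair that the harm is doubly conditional, on a person-level analysis and on a correlation that affects the comparison, and that many small clusters make it mild (5.5–7.4% with 41 clusters of 5). The largest figures need few clusters and either a single-time comparison or weakly stable cluster effects. These points limit the size, not the direction under positive correlation. Finally, Mancl-DeRouen is somewhat conservative with few clusters; Kauermann-Carroll is nearer nominal but reached 6.0% with unequal sizes.

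**Conclusion.** The concern holds, and the text should be fixed. The protocol allocates by cluster but gives no method the job of handling within-cluster correlation. If the groups are compared at person level, the type I error exceeds its nominal value whenever positive within-cluster correlation affects the comparison. There is no inflation at ICC 0, none for change from baseline when cluster effects are perfectly stable, and little when they are nearly so; a negative ICC would make the test conservative.

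The document supports the direction, not a size. The calculated range, from 5.0% to 25.8%, rests entirely on the assumed ICC, cluster number, autocorrelation and within-person correlation. Confidence is medium because the list is open and the analysis plan may already deal with the point.

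**What to change.** State in the Analysis text that every between-group comparison in the second- and third-year trial accounts for the randomised cluster, by one of:

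- (a) GEE with the cluster as the independent unit;
- (b) a mixed model with random effects for cluster and person, plus cluster-by-time if the effect is group-by-time;
- (c) an analysis of cluster-level summaries.

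When clusters are few, use a t reference with degrees of freedom from the number of clusters, and for (a) also a bias-corrected robust variance such as Mancl-DeRouen or Kauermann-Carroll. Keep person-level chi-square, ANOVA and ordinary regression for the first-year survey and for baseline description. If the statistical analysis plan already says this, a reference to it is enough.

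The change needs wording and a recorded cluster identifier, and no new participants. The real cost is precision. The interval factor is √DEFF × t(0.975, 2k − 2)/1.96; for k = 5 it is 2.306/1.96 = 1.18 at DEFF 1 and √3 × 1.18 = 2.04 at DEFF 3.

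| Clusters per group | Change from baseline (c from 1.0 to 0.5) | One time point |
|---|---|---|
| 5 | 1.18–2.04 | 1.39–2.04 |
| 10 | 1.07–1.51 | 1.17–1.51 |
| 20 | 1.03–1.25 | 1.08–1.25 |

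With few clusters and an ICC near 0, the mixed model with t is conservative (1.6% error at 5 near-equal clusters per group), and Mancl-DeRouen is so to a lesser degree. A real effect could then be missed.
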